9.1 General Principles

The objective of the data screening is to assess the quantity, quality and statistical characteristics of the data relative to the requirements of the planned analyses.

9.2 Data Handling and Electronic Transfer of Data

9.3 Handling of Missing and Incomplete Data

Every effort will be made to obtain complete data in the clinical study. Partial or missing dates of adverse events and concomitant medications will be imputed. Adverse events with missing IP relatedness, seriousness, or CTCAE severity grades are included in TEAE as long as the events qualify for the reporting period. Events with missing relatedness, seriousness, and severity grades will be excluded from treatment-related, serious, and with a CTCAE grade of 3 or higher AE analysis, respectively. [REDACTED]

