9.2 Safety Event Reporting Procedures

9.2.1 Adverse Events

9.2.1.1 Reporting Procedures for Adverse Events That do not Meet Serious Criteria

The investigator is responsible for ensuring that all adverse events observed by the investigator or reported by the subject that occur after first dose of talimogene laherparepvec/placebo or pembrolizumab through the safety follow-up visit (ie, 30 [+7] days after the last dose of talimogene laherparepvec/placebo or pembrolizumab, whichever is later, are reported using the applicable CRF (eg, Adverse Event Summary). In addition, injected investigational product-related adverse events that occur during the long term safety follow-up period until the end of study should also

be captured in the Adverse Event CRF although these events will not be considered treatment-emergent adverse events.

The investigator must assign the following adverse event attributes:

- Adverse event diagnosis or syndrome(s), if known (if not known, signs or symptoms),
- Dates of onset and resolution (if resolved),
- Severity [and/or toxicity per protocol],
- Assessment of relatedness to injected investigational product and/or pembrolizumab, and
- Action taken.

The adverse event grading scale used will be the CTCAE version 4.0. The grading scale used in this study is described in [Appendix A](#). The investigator must assess whether the adverse event is possibly related to injected investigational product and/or pembrolizumab. This relationship is indicated by a “yes” or “no” response to the question: Is there a reasonable possibility that the event may have been caused by injected investigational product and/or pembrolizumab?

The investigator must assess whether the adverse event is possibly related to any study-mandated activity and/or procedure (including any screening procedures). This relationship is indicated by a “yes” or “no” response to the question: “Is there a reasonable possibility that the event may have been caused by a study activity and/or procedure”?

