If event occurred before the first dose of Investigational Product (IP)/drug under study, add a check mark in the corresponding box.

Is event serious?* – Indicate Yes or No. **This is a mandatory field.**

Serious Criteria Code* – **This is a mandatory field for serious events.** Enter all reasons why the reported event has met serious criteria:

- Immediately life-threatening – Use only if the subject was at immediate risk of death from the event as it occurred. Emergency treatment is often required to sustain life in this situation.
- If the investigator decides an event should be reported in an expedited manner, but it does not meet other serious criteria, "Other Medically Important Serious Event" may be the appropriate serious criterion.

Relationship to IP – The Investigator must determine and enter the relationship of the event to the IP at the time the event is initially reported. **This is a mandatory field.**

Relationship to Amgen device* – The Investigator must determine and enter the relationship of the event to the Amgen device (e.g. prefilled syringe, auto-injector) at the time the event is initially reported. **If the study involves an Amgen device, this is a mandatory field. This question does not apply to non-Amgen devices used in the study (e.g. heating pads, infusion pumps)**

Outcome of Event* – Enter the code for the outcome of the event at the time the form is completed. **This is a mandatory field.**

- Resolved – End date is known
- Not resolved / Unknown – End date is unknown
- Fatal – Event led to death

If event is related to a study procedure, such as a biopsy, radiotherapy or withdrawal of a current drug treatment during a wash-out period, add a check mark to the corresponding box. This does not include relationship to IP or concomitant medication – only diagnostic tests or activities mandated by the protocol.

4. Hospitalization

If the subject was hospitalized, enter admission and discharge dates. Hospitalization is any in-patient hospital admission for medical reasons, including an overnight stay in a healthcare facility, regardless of duration. A pre-existing condition that did

not worsen while on study which involved a hospitalization for an elective treatment, is not considered an adverse event. Protocol specified hospitalizations are exempt.

Completion Instructions - Electronic Adverse Event Contingency Report Form
(for use for Studies using Electronic Data Capture [EDC])

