10.6 Safety Analyses

10.6.1 Adverse Events

Safety analyses will be conducted separately for phase 1b and phase 3. The Medical Dictionary for Regulatory Activities (MedDRA) version 20.0 or later will be used to code all adverse events (AE) to a system organ class and a preferred term. The CTCAE version 4.0 **or later** will be used to grade severity of adverse events. In general, events with missing IP relatedness, seriousness, or CTCAE severity grades are included in the analysis of treatment emergent AE as long as the event is satisfied for a TEAE.

However, analyses of treatment-related, SAE, or grade 3 or higher, or combination thereof will exclude events with missing relatedness, seriousness, and severity grades, respectively.

The subject incidence of AEs will be summarized for all treatment-emergent AEs, serious AEs, AEs leading to withdrawal of investigational product, grade 3 or 4 AEs, fatal AEs, talimogene laherparepvec events of interest (EOI) and pembrolizumab events of clinical interest (ECI). Subject incidence of EOIs and ECIs will be summarized by the EOI categories and ECI categories. Preferred terms within each EOI and ECI category will also be summarized.

The subject incidence of all treatment-related AEs, serious AEs, AEs leading to withdrawal of investigational product, grade ≥ 3 AEs, and fatal AEs will be tabulated by system organ class and preferred term in descending order of frequency.

Summaries of treatment-emergent and serious AEs occurring in at least 5% of the subjects by preferred term in any treatment arm will be provided in descending order of frequency.

A listing of fatal AEs will be provided. A listing of SAEs/EOIs/ECIs reported in the clinical database with an event onset after 30 days since last dose of IP will be provided. Listing of SAEs from consent and before first dose of study therapy will also be provided separately. Listing of SAEs reported with event onset 90 days after the last dose of study therapy or 30 days after last dose of study therapy if the subject initiates new anticancer therapy, whichever is earlier, will be provided. Additional listings of SAEs/EOIs/ECIs for subjects who received treatment by error that occur during the incorrect treatment period will be provided.

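### Adverse events with a blank relatedness, seriousness or grade are dropped from the matching related, serious or grade 3+ table, which can lower but never raise each arm's incidence there

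*SAP*

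**What the plan says.** SAP 9.3 handles missing adverse event attributes in two steps. It first retains the events in the overall count: "Adverse events with missing IP relatedness, seriousness, or CTCAE severity grades are included in TEAE as long as the events qualify for the reporting period". It then removes them from the narrower tables: "Events with missing relatedness, seriousness, and severity grades will be excluded from treatment-related, serious" and grade 3 or higher analyses, with the word respectively closing the sentence. A blank grade therefore takes an event out of the grade 3 or higher analysis only, and the other two fields work the same way.

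SAP 10.6.1 repeats both steps and adds tables that cross two attributes: "However, analyses of treatment-related, SAE, or grade 3 or higher, or combination thereof will exclude events with missing relatedness, seriousness, and severity grades, respectively".

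Missing dates are treated differently in the same paragraph of 9.3: "Partial or missing dates of adverse events and concomitant medications will be imputed". No imputation of relatedness, seriousness or grade is visible. A redaction follows the rule in 9.3; the restatement in 10.6.1 carries no visible qualification.

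On collection, Protocol 9.2.1.1 states "The investigator must assign the following adverse event attributes", and the list that follows includes severity and relatedness. The contingency form for serious events in Protocol Appendix B states "The Investigator must determine and enter the relationship of the event to the IP at the time the event is initially reported", and it also marks seriousness as a mandatory field. Protocol 12.3 describes a data review that looks for omissions and raises queries to sites.

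**The concern.** Treatment-related events, grade 3 or higher events and serious events are named phase 3 secondary endpoints (Protocol 10.1.1.2, SAP 4.1.2). In the tables that report them, leaving out an event with a blank field has the same effect as coding it on the favourable side.

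For tumour response the plan does the reverse: a subject with no post-baseline assessment counts as a non-responder (SAP section 6, Protocol 10.5.3). The sensitivity analyses in SAP 10.5.4 concern efficacy. No count of events with missing attributes and no worst-case safety table is visible. From the planned output alone, a reader could not tell whether the rule touched no subjects or several. What is at stake is the accuracy of three descriptive safety incidences and of the comparison between arms drawn from them. Type I error, power and the primary endpoints are not involved.

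**Working it through.** The documents give no missing-attribute rate and no figure that depends on one, so there is no plan figure to reproduce. The direction can be derived, and the size can be shown only under assumptions.

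**Direction within one arm.** Let p be the true subject incidence of a qualifying event (for example, at least one grade 3 or higher event). Let m be the share of those subjects whose only qualifying event lacks the field.

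- Reported incidence = p × (1 − m), which is at most p.
- It equals p when nothing is missing, when each affected subject has another qualifying event with the field complete, or when the blank event would not have qualified anyway.
- Overall treatment-emergent incidence does not change, because the events stay in that table.

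**Direction between arms.** Reported difference = p1(1 − m1) − p2(1 − m2). Its error relative to p1 − p2 is p2·m2 − p1·m1, which can have either sign.

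**Illustration.** Inputs:

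- 330 subjects per arm, from Protocol 10.2.2.
- Grade 3 or higher incidences of 36% and 21%, from the earlier phase 3 study of talimogene laherparepvec versus GM-CSF described in Protocol 2.2. They are borrowed for scale only, since the comparator and background therapy differ.
- m from 0 to 5%. This range is an assumption.

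| m, arm 1 / arm 2 | Arm 1 reported | Arm 2 reported | Difference (points) | Subjects dropped |
|---|---|---|---|---|
| 0 / 0 | 36.00% | 21.00% | 15.00 | 0 / 0 |
| 1% / 1% | 35.64% | 20.79% | 14.85 | 1.2 / 0.7 |
| 5% / 5% | 34.20% | 19.95% | 14.25 | 5.9 / 3.5 |
| 5% / 0 | 34.20% | 21.00% | 13.20 | 5.9 / 0 |
| 0 / 5% | 36.00% | 19.95% | 16.05 | 0 / 3.5 |

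Example, fourth row: 36% × 0.95 = 34.20%; 34.20 − 21.00 = 13.20 points; 330 × 0.36 × 0.05 = 5.9 subjects.

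Over this range the largest loss within an arm is 1.8 percentage points (36.0 − 34.2). The difference between arms runs from 13.20 to 16.05 points against a true 15.00.

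**The case against.** The strongest reply has four parts.

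- **The events are still reported.** A reader who sees only the exclusion sentence might infer that these events disappear from the safety report. They do not: the sentence before it keeps them in the treatment-emergent tables, and one blank field affects only its own table and the combinations. The exclusion sentences also do not name the overall fatal-event summary or the listing of fatal events. This part stands in full.
- **The comparison is not biased in one direction.** A reader might also infer that the rule can only understate the toxicity of the combination. The phase 3 safety objective compares the combination with placebo plus pembrolizumab (Protocol 1.2, SAP 2.2), and that difference can be overstated if more fields are blank in the placebo arm. The one-directional statement holds only within an arm.
- **Missingness should be rare.** The investigator must assign severity and relatedness, the serious-event form makes relatedness and seriousness mandatory, and omissions are queried. This supports expecting a small effect. It does not show that the effect is zero, and the SAP itself provides for the case where fields remain blank.
- **Coding every blank to the worst category has its own error.** SAP section 6 defines a serious event by the investigator's determination. Counting blank flags as serious in the main tables would report serious events that no investigator had declared, and blank grades coded as grade 3 would be severe by default. This is a good reason to leave the main serious and grade 3 or higher tables alone. It is no argument against a supplementary table.

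The redaction after the rule in 9.3 may hide further handling text, so the absence of a count or sensitivity table can be described only as not visible.

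**Conclusion.** The point holds as a minor one about safety reporting. The rule is stated twice and is clear. In the treatment-related, serious and grade 3 or higher tables and their combinations it can lower an arm's incidence or leave it unchanged, and nothing visible lets the reader judge by how much. The difference between arms can err in either direction.

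The size is unknown, because no missing rate is given, and is probably small given mandatory entry and queries. If 1% of qualifying subjects depend on an event with a blank field, about one subject per arm is affected. The 5% rows in the working show the edge of an assumed range and are not an expectation. These figures rest on borrowed incidences and on 330 treated subjects per arm.

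The documents do not support a claim that events are lost from the safety report, or that the added toxicity of the combination is necessarily understated.

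**What to change.** Amend SAP 9.3 and 10.6.1 as follows.

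1. Count an event with missing relatedness as related in the treatment-related tables.
2. Report, by arm, the number of events missing each of relatedness, seriousness and grade.
3. Add one prespecified worst-case table that counts missing seriousness as serious and missing grade as grade 3 or higher. Leave the main serious and grade 3 or higher tables as they are, so that the main and worst-case figures together bracket each arm's incidence.

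The cost is one or two SAP sentences and one more safety table. Treatment-related incidence may rise slightly and could include some events that are in fact unrelated. If queries resolve every field, the counts are zero and the worst-case table matches the main tables.

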9.4 Detection of Bias

Lack of protocol compliance may introduce potential bias in the estimation of protocol endpoints. All important protocol deviations (IPDs) will be reported, documented and stored in eClinical (a clinical trial management system). IPD reports will be produced [REDACTED] by the study manager and will be regularly reviewed in the study team's IPD review meetings as well as before analysis.

Protocol compliance will be examined by tabulating subjects with IPDs. Bias will be evaluated, in part, by conducting sensitivity analyses using the Per Protocol Analysis Set (see [Section 7.7](#)).

9.5 Outliers

Descriptive statistics will be used to identify potential outliers in key variables. Suspected outliers will be included in all analyses unless there is sufficient scientific justification to exclude them.

9.6 Distributional Characteristics

All binary endpoints will follow a binomial distribution. A beta prior is assumed in the Bayesian model for the interim iORR/iDCR futility analysis. The KM estimates for the probability of time-to endpoints are based on non-parametric methods. Treatment comparisons in time-to endpoints based on the Cox proportional hazards (PH) model are semi-parametric. Assumption of proportionality in hazards will be examined graphically with the Schoenfeld residuals plot (see code fragment in [Appendix C](#)). Comparisons based on the log-rank test are fully non-parametric.

Should there be inferential statistics for continuous variables that rely on the normal distribution assumption, the assumption will be checked using a normal probability plot. If severe departure from normality is observed, a non-parametric method such as the Wilcoxon rank sum test will be employed.

9.7 Validation of Statistical Analyses

Programs will be developed and maintained and output will be verified in accordance with current risk-based quality control procedures.

Tables, figures and listings will be produced with validated standard macro programs where standard macros can produce the specified outputs.

The production environment for statistical analyses consists of Amgen-supported versions of statistical analysis software, for example the SAS System version 9.4 or later and qualified R.

10. Statistical Methods of Analysis

10.1 General Principles

In general, the efficacy and safety analyses will be conducted separately for phase 1b and phase 3. Data collected after the analysis data cutoff date at each analysis time will be excluded.

For phase 1b, descriptive statistics for the confirmed ORR, BOR, DCR, DRR, DOR, PFS, and OS will be provided where tumor response evaluations are based on investigator assessments using modified irRC. The analysis will include data from phase 1b subjects in the Safety Analysis Set.

For phase 3, the efficacy analyses will be conducted on the Full Analysis Set. Treatment effects on efficacy endpoints will be evaluated and compared between the 2 treatment arms according to the treatment as randomized. Formal treatment comparisons will be performed on the dual primary endpoints and the 3 key secondary endpoints.

Mean, standard deviation, median, first and third quartiles, minimum and maximum will be calculated for continuous variables; frequency count and percent will be calculated for binary and categorical variables. For binary endpoints, proportions and the corresponding 95% confidence intervals, and p-values will be based on normal approximations and the treatment comparison (ratio of proportions, treatment over control) will be based on Cochran-Mantel-Haenszel test (see code fragment in [Appendix C](#)) stratified by randomization stratification factors and baseline PD-L1 status as the primary method. Additionally, p-values from the stratified Mantel-Haenszel test for the common risk difference will also be calculated (see code fragment in [Appendix C](#)). Exact confidence intervals (Clopper & Pearson 1934) (see code fragment in [Appendix C](#)) and Fisher exact tests (see code fragment in [Appendix C](#)) for binary endpoints will be considered for phase 1b and all subgroup analyses in phase 3. Logistic regression will be used to estimate the odds ratio, 95% CI for the odds ratio, and p-value (see code fragment in [Appendix C](#)).

██ time-to-event endpoints will be analyzed as follows. Time to-event endpoints will be summarized descriptively by treatment group using the Kaplan-Meier (K-M) method. Standard errors of estimated treatment differences by time point will be calculated using Greenwood's formula (Kalbfleisch and Prentice, 1980). KM median estimates will be provided for each treatment arm along with KM estimates at appropriate times for each endpoint (eg, month 3, month 6, month 9, month 12, etc for PFS and 1 year, 2 year, 3 year etc. for OS). In addition, the point estimate of the adjusted risk difference (difference in Kaplan-Meier estimates at the time point of interest, treatment arm – control arm) and the corresponding 95% confidence interval will be provided using the inverse variance-weighted method (see code fragment in [Appendix C](#)). Stratified log-rank test statistics and associated p-values will also be used as the primary analysis method to assess the hypothesis of no treatment difference. Hazard ratios will be estimated using stratified Cox proportional hazards (PH) models (see code fragment in [Appendix C](#)).

For stratified analyses, the stratification factors will include randomization stratification factors per IVRS and PD-L1 status at baseline (positive vs not positive). The criteria for PD-L1 status is as follows:

- Any available PD-L1 positive result makes the subject a positive (irrespective of tissue analyzed and irrespective of the timing).
- If there are more than one PD-L1 result, and none of them are positive, then choose the one from a fresh biopsy.

Listings (eg, baseline characteristics, adverse events and exposure) of subjects in the Retreatment Analysis Set will be provided.

